^e For the [REDACTED] in cycle 1, PK samples should be collected pre-infusion and 2, 6, 24, 48, and 72 hours after start of infusion.

^f For the [REDACTED] in cycle 1, PK samples should be collected pre-infusion and 2, 6, 24, and 48 hours after start of infusion.

^g For the [REDACTED] in cycle 1, PK samples should be collected pre-infusion and 2, 6, 24, 48, 72, 96, and 120 hours after start of infusion.

Table 1-6. Schedule of Imaging Assessments (Cycle Independent)

	SCR	Treatment Period ^a		EOT	SFU	LTFU	Notes
MRI brain	X						All subjects must have MRI of the brain performed within 28 days prior to the first dose of AMG 160. All brain scans on protocol are required to be MRI unless MRI is contraindicated, then CT with contrast is acceptable. Subsequently, MRI brain can be performed at any time if clinically indicated per standard of care.
CT/MRI and tumor burden assessment (chest, abdomen and pelvis)	X	Weeks 1-24 Every 8 weeks	Weeks 25+ Every 8 weeks	X	X	X ^b	Radiologic imaging (CT/MRI) is required at the EOT or SFU visit if the subject has not had radiologic imaging performed within 6 weeks of the visit.
⁶⁸ Ga-PSMA-11 PET/CT	X	At week 8 and week 16		X			

CT = computed tomography; EOT = end of treatment; ⁶⁸Ga = 68-Gallium; [REDACTED]; LTFU = longterm follow-up; MRI = magnetic resonance imaging; PET = positron emission tomography; PSMA = prostate-specific membrane antigen; RECIST = Response Evaluation Criteria in Solid Tumors; SCR = screening; SFU = safety follow-up;

^a Timing is based on first dose of AMG 160 (cycle 1 day 1) ± 7 days for imaging assessments.

^b For subjects who discontinued treatment for any reason other than confirmed disease progression, every effort should be made to perform radiographic imaging (CT/MRI) of the chest, abdomen, pelvis, and all other known sites of disease every 3 months until documentation of confirmed disease progression per modified RECIST 1.1, clinical progression, start of new anticancer therapy, or up to 3 years after the first dose of AMG 160, whichever occurs first.

2. Introduction

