8.2.2 Efficacy Assessments

Efficacy will be determined by radiographic assessments.

Radiographic assessments will be obtained as scheduled in [Table 1-6](#) irrespective of cycle duration including dose delays and treatment discontinuation.

Standard radiological assessments should take place until clinically significant disease progression or deterioration, withdrawal of consent, or start of new anticancer therapy. Every assessment must include the chest, abdomen, and pelvis, all other known sites of disease and magnetic resonance imaging (MRI) of the brain if a subject has signs or symptoms suggestive of CNS metastases. The MRI/CT can be obtained earlier if clinical deterioration necessitates an earlier scan at the discretion of the managing physician. The same contrast and modality used at screening should be used for all subsequent assessments. [REDACTED]

[REDACTED]

Tumor burden assessments will be performed based on modified RECIST 1.1 criteria. To confirm PD, a second MRI/CT scan must be performed 4 to 6 weeks after the first detection of radiographical progression. Responses (PR and complete response [CR]) require confirmation by a repeat consecutive assessment at least 4 weeks after the first detection of radiographical response. Refer to the imaging manual for details on imaging assessments.

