 - Subjects with a global deterioration of health status requiring discontinuation of treatment prior to radiologic confirmation of disease progression should have the reason for treatment discontinuation classified as 'clinical disease progression' not 'radiographic progressive disease'. Every effort should be made to radiologically confirm progression even after discontinuation of treatment.

Summary of Measurement and Tumor Response Assessment Based on Modified RECIST 1.1	
Measurable lesions	
 Non-nodal lesions: ≥ 10 mm (unidimensional measurement) Pathologic lymph nodes: longest diameter short axis ≥ 15 mm
Measurement of each lesion	
 Non-nodal lesions: The longest diameter (mm) in the axial plane Pathologic lymph nodes: short axis (mm)
Tumor burden	
 Sum of the longest diameters (SLD) of all target lesions Up to 5 lesions per organ, up to 10 total
Response assessment: target lesions (calculated from % change in tumor burden)	
 CR: Disappearance of all lesions 
 Pathologic lymph nodes short axis < 10 mm PR: $\geq 30\%$ decrease from baseline SD: Does not meet criteria for CR, PR or progressive disease. Progressive disease: $\geq 20\%$ increase (and ≥ 5 mm absolute increase) from nadir
Response assessment: non- target lesions	
 CR: Disappearance of all lesions 
 Pathologic lymph nodes short axis < 10 mm SD: Persistence of one or more non-target lesion(s) Progressive disease: Unequivocal progression of existing non-target lesions
New Lesions	The presence of new lesion(s) defines progression
Confirmation	Confirmation by subsequent assessment after ≥ 4 weeks required for CR, PR and progressive disease.

Summary of modified RECIST 1.1 Overall Response Assessment			
Target lesions (tumor burden) ^a , %	Non- target lesions	New lesions	Overall Response using modified RECIST 1.1
↓ 100%	Absent	Absent	CR ^b
None ^d	Absent	Absent	CR ^b
↓ 100%	Present	Absent	PR ^b
↓ $\geq 30\%$	Absent/Present	Absent	PR ^b
↓ $< 30\%$ to ↑ $< 20\%$	Absent/Present	Absent	SD
None ^d	Present	Absent	SD
↑ $\geq 20\%$	Any	Any	Progressive disease ^c
Any	Unequivocal progression	Any	Progressive disease ^c
Any	Any	Present	Progressive disease ^c
NA/ND/UE	Absent/Present	Absent	UE
None ^d	NA/ND/UE	Absent	UE

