Details about the censoring rules are included in [Appendix E](#).

Radiographic Progression:

Disease progression per RECIST 1.1 occurs.

Radiographic Progression-free Survival (radiographic PFS):

Radiographic PFS is defined as the interval from Study Day 1 to the earlier of a radiographic progression or death from any cause; otherwise **PFS is censored based on criteria in [Appendix E](#)**.

Clinical Progression:

Clinical disease progression is based on clinical symptoms and are not associated with radiologic progression.

This is recorded by the field ‘disease progression is equal to clinical progression’ on the EOIP eCRF page.

Details about the censoring rules are included in [Appendix E](#).

Clinical Progression-free Survival (clinical PFS):

Clinical PFS is the time from Study Day 1 to clinical disease progression or death from any cause.

Details about the censoring rules are included in [Appendix E](#).

Time to Response (TTR):

TTR is defined as the time from the date of Study Day 1 to the date of the first documented CR or PR that is subsequently confirmed per RECIST1.1. For a subject who did not respond, time to response will be censored at the latest evaluable radiological assessment date. If a subject has no tumor evaluation in the study, time to response will be censored at the date of Study Day 1.

The time of the initial response will be defined as the earliest of the dates contributing towards the first visit response of PR or CR.

- For confirmed responders whose PR or CR are confirmed in two **evaluable** assessments, the first PR/CR assessment among the two **evaluable** assessments will be used to calculate TTR.
- For unconfirmed responders awaiting follow-up confirmation scans, the PR or CR assessment that is awaiting confirmation scan will be used to calculate TTR.

Time to Radiographic Progression:

Time to radiographic progression is defined as the interval from Study Day 1 to radiographic progression; otherwise, time to radiographic progression is censored based on the criteria in [Appendix E](#).

Time to Clinical Progression:

Time to clinical progression is defined as the interval from Study Day 1 to clinical progression; otherwise, time to clinical progression is based on the criteria in [Appendix E](#).

Subsequent Therapy:

Subsequent therapy is defined as subjects receiving anti-cancer therapies intended to treat NSCLC or any other anti-cancer therapies prior to end of study.

Time to Subsequent Therapy:

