Appendix E. Censoring Rules

Censoring rules for PFS or TTP (radiographic):

Situation up to DCO/EOS	Date of Event or Censoring	Outcome
No evaluable post-baseline or on-study disease assessment; On study without PD or death	Date of the first dose of investigational product (AMG 160)	Censored
PD prior to new anti-cancer therapy	Date of PD	Event
No PD, but death recorded without new anti-cancer therapy	PFS: Date of death; TTP: Date of last evaluable radiographic tumor assessment	PFS: Event; TTP: Censored
Start of new anti-cancer therapy prior to PD or death, or prior to any other disease assessment if there is no PD or death recorded	Date of last evaluable radiographic tumor assessment prior to the start of new anti-cancer therapy	Censored
No PD or death, no new anti-cancer therapy	Date of last evaluable radiographic tumor assessment	Censored
Death or PD immediately after more than one consecutively missed tumor assessment**	Date of last evaluable radiographic tumor assessment prior to the missing assessments*	Censored

DCO: data cutoff; EOS: end of study; PD: progressive disease

* This supersedes the previous rules that result in Event at date of PD or death

**Implementation details: censoring with death or PD immediately after more than one consecutively missed tumor assessment

Scenarios of PD or Death	Censoring Rule	X Days in Censoring Rule
While on treatment	If PD or death is X days after the last scan, censor at the last scan	119

Censoring rules for Duration Of Response (CT/MRI assessment):

Situation up to DCO/EOS	Date of Event or Censoring	Outcome
PD prior to new anti-cancer therapy	Date of PD	Event
No PD, but death recorded without new anti-cancer therapy	Date of death	Event
Start of new anti-cancer therapy prior to PD or death, or prior to any other disease assessment if there is no PD or death recorded	Date of last evaluable tumor assessment by CT/MRI prior to the start of new anti-cancer therapy	Censored
No PD or death, no new anti-cancer therapy	Date of last evaluable tumor assessment by CT/MRI	Censored
Death or PD immediately after more than one consecutively missed tumor assessment**	Date of last evaluable tumor assessment by CT/MRI prior to the missing assessments*	Censored

DCO: data cutoff; EOS: end of study; PD: progressive disease

* This supersedes the previous rules that result in Event at date of PD or death

**Implementation details: censoring with death or PD immediately after more than one consecutively missed tumor assessment

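### The protocol disagrees with itself on imaging after clinical progression, and the SAP has no rule for these subjects in radiographic PFS and TTP; the upward bias is small if the EOT/SFU scan is done, larger if it is missed

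*Protocol*

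**What the plan says.** **Protocol, Table 1-6 footnote b.** For subjects who stopped treatment for any reason other than confirmed progression, CT/MRI continues "every 3 months until documentation of confirmed disease progression per modified RECIST 1.1, clinical progression, start of new anticancer therapy", or for up to 3 years from first dose, whichever comes first.

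**Protocol, Section 8.2.2.** "Standard radiological assessments should take place until clinically significant disease progression or deterioration, withdrawal of consent, or start of new anticancer therapy". The same section says scans follow Table 1-6 "irrespective of cycle duration including dose delays and treatment discontinuation".

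**Protocol, Section 11.12 (Appendix 12).** A subject who must stop treatment for global deterioration before progression is radiologically confirmed is classed as a clinical progressor. The text then adds: "Every effort should be made to radiologically confirm progression even after discontinuation of treatment".

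**Protocol, Table 1-6, notes column.** "Radiologic imaging (CT/MRI) is required at the EOT or SFU visit if the subject has not had radiologic imaging performed within 6 weeks" of that visit.

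**SAP, Section 5.1.2.** "Radiographic PFS is defined as the interval from Study Day 1 to the earlier of a radiographic progression or death from any cause". Clinical progression is kept apart: "Clinical disease progression is based on clinical symptoms and are not associated with radiologic progression". It is read from the EOIP eCRF page and feeds only the clinical PFS and clinical TTP endpoints.

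**SAP, Appendix E.** The radiographic PFS/TTP table has rows for PD, death, new therapy, no event and missed assessments. It has none for clinical progression. Under the new-therapy row the subject is censored at "Date of last evaluable radiographic tumor assessment prior to the start of new anti-cancer therapy".

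**The concern.** The event that ends imaging in Table 1-6 and Section 8.2.2 is the one after which Appendix 12 asks for more imaging, and neither place refers to the other. About 12 sites are planned (5 in Part 1 plus 7 in Part 2, Section 4.2.2). They can follow different passages, and a scan not taken cannot be recovered later.

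Subjects who deteriorate are those most likely to show radiographic PD on the next scan. If that scan is not taken, their event is delayed to death or replaced by censoring. Kaplan-Meier assumes that a censored subject has the same outlook as those still at risk, which fails here. The curves for radiographic PFS and TTP, both secondary endpoints, would sit too high, and more so the more often progression is recognised clinically.

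**Working it through.** **1. The plan's own number.** The only stated figure that bears on this is X = 119 days in the Appendix E missed-assessment rule. It reproduces as two 8-week intervals plus the 7-day window: 2 × 56 + 7 = 119. The SAP does not show this derivation. The value is given only for subjects on treatment, so a death after a scan gap off treatment has no stated X.

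**2. What Appendix E does with a clinical progressor who has no later PD scan.**

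| Situation | Radiographic PFS | Radiographic TTP |
|---|---|---|
| Dies, no new therapy | Event at death, unless the missed-assessment row applies | Censored at last evaluable scan |
| Starts new therapy | Censored at last scan before it | Same |
| Alive, no new therapy | Censored at last evaluable scan | Same |

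Each row delays the event or removes it, so the estimate can only be pushed upward.

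**3. Size, main model.** Inputs from the documents: n = 40, scans every 8 weeks, EOT/SFU scan if none within 6 weeks, SFU about 30 days after last dose, 3-monthly follow-up imaging. Assumptions not in the documents: median time to progression 3 months, median survival after clinical progression 3 months, clinical share 10%, 20% or 30%, and PD visible on a scan taken after deterioration. Simulated 6-month radiographic PFS (%), no new therapy:

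| Imaging after clinical progression | 10% | 20% | 30% |
|---|---|---|---|
| None at all | 31 | 34 | 37 |
| Table 1-6 as written, EOT/SFU scan done | 28.9 | 30.0 | 31.0 |
| The same plus 3-monthly scans (stop clause removed) | 28.2 | 28.6 | 28.8 |
| Effect of the stop clause (row 2 minus row 3) | 0.7 | 1.4 | 2.2 |

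- For TTP the clause adds about 0.5-1.5 points.
- If half start new therapy, the PFS effect is about 0.4, 0.7 and 1.2 points.
- If the 6-week rule is applied at EOT only, about 21% of clinical progressors get the scan, against about 60% with both visits. The clause is then worth about 1-4.5 points.
- A scan at the time of deterioration gives about 27-28%. No imaging at all exceeds that by about 3-10 points for PFS and 4-15 for TTP.
- The standard error at n = 40 is √(0.28 × 0.72 / 40) = 0.071, about 7 points.

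**4. Sensitivity to the model.** A second simulation assumed median progression at 120 days, clinical progression a mean 28 days before RECIST PD, median survival 90 days after clinical progression, and continued imaging every 8 weeks. At clinical shares of 10%, 20% and 30% with no new therapy, the excess at 26 weeks over continued imaging was:

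- PFS with the EOT/SFU scan: 38.9 − 38.1 = 0.8; 39.7 − 37.8 = 1.9; 40.1 − 37.6 = 2.5 points. With no scan: 1.6, 3.0 and 4.2.
- TTP with the EOT/SFU scan: 46.8 − 45.6 = 1.2; 49.3 − 46.0 = 3.3; 50.6 − 46.2 = 4.4 points. With no scan: 2.6, 5.5 and 8.0.

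The direction is the same in every scenario. The size depends on whether the EOT/SFU scan is taken and whether PD is already measurable then.

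**The case against.** A reader might infer that, under Table 1-6, clinical progressors never have a radiographic PD. The documents do not support that, for two reasons. First, Table 1-6 itself requires a scan at EOT or SFU when none was done within 6 weeks, and Section 8.2.2 allows an earlier scan when deterioration calls for one. Second, the Appendix 12 sentence sits under the rule for confirming PD on a second scan, so it also covers subjects who already have a first PD scan. SAP Section 5.1.2 defines radiographic progression simply as progression per RECIST 1.1, and Appendix C drops the confirmation requirement for best-response endpoints. Those subjects therefore appear to be events whichever passage is followed.

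A reader might also attribute the full 3-10 point PFS gap to the stop clause. That gap compares no imaging with a scan on the day of deterioration, which no passage requires. With 3-month median survival, about half of these subjects die before a first 3-monthly scan, so removing the clause recovers little beyond the EOT/SFU scan.

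It is also fair to say that clinical PFS and clinical TTP report these subjects separately, that no hypothesis is tested (SAP Section 2.2), and that the futility rule uses ORR. All of this stands and limits the size and the consequence. It does not reconcile the three passages, and it leaves the radiographic estimates without any check on the bias.

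**Conclusion.** The contradiction is real and the direction of bias is upward for both radiographic endpoints. In the main model, with the EOT/SFU scan done at either visit, the stop clause adds about 1-2 points to 6-month radiographic PFS and about 0.5-1.5 to TTP. That is well inside the 7-point standard error, but it is systematic. The second model puts TTP somewhat higher, at about 1-4 points. If the scan is missed, the excess over a scan at deterioration reaches about 3-10 points for PFS and 4-15 for TTP. All sizes rest on assumed clinical shares and medians; the documents give none.

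The upward bias concerns the Kaplan-Meier estimate. It should not be read as saying that each affected subject's recorded time is longer: a censored subject's time is shorter. Scans taken after new therapy starts do not count under Appendix E, so the passage followed matters only before then. No decision rule is affected.

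**What to change.** **Protocol.** Reconcile Table 1-6 footnote b, Section 8.2.2 and Appendix 12 so that they give one instruction on imaging after clinical progression. Keep the other stops: confirmed radiographic progression (retaining the word confirmed, because a confirmation scan is required), new anticancer therapy, withdrawal of consent and 3 years.

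**SAP, Appendix E.** Add a sensitivity analysis of radiographic PFS and TTP that counts clinical progression recorded on the EOIP eCRF page as an event on its date.

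**Cost.** Edits to three protocol passages and one more descriptive analysis from data already collected. The EOIP page will not capture clinical progression that arises after a subject stopped treatment for another reason, and some deteriorating subjects will still miss scans whatever the text says.

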2.1 Study Rationale

AMG 160 (acapatamab) is a novel half-life extended (HLE) bispecific T-cell engager (BiTE[®]) molecule designed to redirect T effector cells to lyse prostate-specific membrane antigen (PSMA)-expressing cells, with a single chain fragment crystallizable (scFc) moiety for half-life extension. AMG 160 induces potent T cell redirected lysis of prostate cancer cells, with half-maximal effective concentrations of 6-55 pM against prostate cancer cell lines in vitro that express as low as 6881 PSMA copies per cell (Bailis et al, 2019). The BiTE mechanism of action is effective against even very low levels of target (< 1000 copies per cell; Owen et al, 2019). PSMA has been shown to be highly expressed in metastatic and castration-resistant prostate cancer (von Eyben et al, 2018). Immunohistochemical analysis has shown intense and homogenous expression of PSMA on prostate cancer cells within metastatic lesions localized to the bones, lymph nodes, soft tissue and the lungs (Chang et al, 2001; Sweat et al, 1998; Murphy et al, 1996). Numerous PSMA-targeted therapies in prostate cancer are currently under development. PSMA has also been shown to be expressed on the surface of endothelial cells within the tumor vasculature of many tumor types, including non-small cell lung cancer (NSCLC), and is not expressed in the vasculature of normal endothelial tissues (Chang et al, 1999). Several recent reports confirm PSMA expression on the tumor vasculature of NSCLC, with recent studies showing 49-77% of NSCLC samples noting PSMA expression in the tumor vasculature (Schmidt et al, 2017; Wang et al, 2015). PSMA-targeted radioligands have also shown the potential to identify PSMA-positive lung cancer. (Shetty et al, 2016; Milowsky et al, 2007). In vitro, PSMA expression can be induced on endothelial cells cultured in conditioned media from cancer cell lines (Nguyen et al, 2016; Liu et al, 2011). In vivo, angiogenesis was significantly impaired in PSMA-null mice or PSMA wild-type mice treated with a PSMA inhibitor, suggesting that PSMA participates in tumor-specific neovasculature growth (Nguyen et al, 2016; Conway et al, 2006). Targeting of PSMA with a radiolabeled PSMA-ligand demonstrates selective killing of PSMA-positive neovasculature in preclinical models (Morgenroth et al, 2019). Previous studies have shown that angiogenesis inhibitors can inhibit tumor growth by blocking new blood vessel formation and depriving the tumor of critical nutrients. More recent studies suggest anti-angiogenesis treatments may enhance immune responses by altering the tumor microenvironment (Fukumura et al, 2018). AMG 160 has the potential both to redirect T cells to lyse any PSMA-positive endothelial cells in tumor vasculature, and to promote

T cell proliferation. This is a phase 1b study to assess safety, tolerability, pharmacokinetics (PK) and anti-tumor activity of AMG 160 in adult subjects with NSCLC.

2.2 Background

2.2.1 Disease

Lung cancer is the leading cause of cancer-related mortality world-wide, with NSCLC accounting for 85% of lung cancer cases (Brahmer et al, 2018). In the United States, lung cancer-related deaths will account for an estimated 142670 deaths in 2019. NSCLC accounts for approximately 85% of all primary lung cancers, with most patients presenting with advanced, unresectable disease at the time of diagnosis (Arbour et al, 2019). Until recently, cytotoxic chemotherapy has been considered the mainstay of treatment for advanced NSCLC. More recently, however, the development of immunotherapy treatments that disrupt the programmed cell death-1 (PD-1) and PDL1 pathway, commonly referred to as immune checkpoint inhibitors, have changed the therapeutic landscape of advanced NSCLC. Developed to target self-tolerance pathways that tumors use to escape immune-mediated recognition and destruction, immune checkpoint inhibitors stimulate T cell-mediated immunity to recognize and destroy cancer cells (Pennock et al, 2015; Reiss et al, 2014). Currently, 4 PD-1 and PDL1 immune checkpoint pathway inhibitors have demonstrated an overall survival (OS) benefit and have been approved either by the United States Food and Drug Administration (FDA) and/or the European Medicines Agency (EMA) for use in patients with NSCLC: nivolumab and pembrolizumab, both targeting the PD-1 receptor, as well as atezolizumab and durvalumab, both targeting the programmed death-ligand 1 (PDL1) (Atezolizumab United States Prescribing Information [USPI]; Pembrolizumab USPI; Nivolumab USPI). Pembrolizumab is approved by the FDA and EMA for patients with metastatic NSCLC whose tumors express PDL1 (tumor proportion score [TPS] \geq 1% per FDA requirements and TPS \geq 50% per EMA requirements), with no epidermal growth factor receptor (EGFR) or ALK genomic tumor aberrations, and no prior systemic chemotherapy treatment for metastatic NSCLC (Pembrolizumab USPI). Pembrolizumab is also approved by the FDA and EMA for use in combination with pemetrexed and platinum chemotherapy, as first-line treatment of patients with metastatic nonsquamous NSCLC, with no EGFR or ALK genomic tumor aberrations and in combination with carboplatin and either paclitaxel or paclitaxel protein-bound, as first-line treatment of patients with metastatic squamous NSCLC (Pembrolizumab USPI). Atezolizumab is approved by the FDA and the EMA for use in combination with bevacizumab, paclitaxel, and carboplatin for the first-line treatment of adult patients with metastatic

non-squamous NSCLC with no EGFR or ALK genomic tumor aberrations (Atezolizumab USPI). In the second line and beyond setting, nivolumab, pembrolizumab (in adults whose tumors express PDL1 with a $\geq 1\%$ TPS), and atezolizumab are all approved by the FDA and the EMA after chemotherapy in patients with metastatic NSCLC (Atezolizumab USPI; Pembrolizumab USPI; Nivolumab USPI).

Molecularly targeted agents have also dramatically altered the therapeutic landscape for a subset of NSCLC patients with EGFR, ALK, NTRK, RET, BRAF, MET mutation, or ROS1 mutations, with multiple tyrosine kinase inhibitors approved by the FDA and/or the EMA for these indications (Russo et al, 2020; Pakkala et al, 2018).

In addition to these recent approvals, anti-angiogenesis inhibitors have demonstrated clinical benefit in patients with NSCLC. Previous studies have shown that tumor angiogenesis plays a key role in supporting tumor growth, the tumor microenvironment and metastatic dissemination (Folkman, 1971). Currently, 3 anti-angiogenesis agents, bevacizumab, ramucirumab and nintedanib, have demonstrated an overall survival benefit and are approved by the FDA and/or EMA for treatment in patients with NSCLC (Ramucirumab USPI; Bevacizumab USPI). Based upon higher rates of hemoptysis associated with squamous cell histology, bevacizumab is currently approved for use in patients with non-squamous NSCLC (Reck et al, 2012; Bevacizumab USPI).

Despite these recent advances, long-term durable responses remain uncommon for the majority of patients with advanced NSCLC, with an estimated 5 year survival of 24%, and remains an unmet need (American Cancer Society, 2020).

2.2.2 Amgen Investigational Product Background: AMG 160

BiTE[®] molecules are designed to direct T effector cells to kill target cells. The BiTE[®] molecule triggers target cell specific cytotoxicity which closely resembles standard cytotoxic T lymphocyte activation. Blinatumomab (BLINCYTO[®]), cluster of differentiation (CD)19 BiTE[®] molecule, is approved for the treatment of acute lymphoblastic leukemia (ALL).

AMG 160 is an HLE BiTE[®] molecule designed to direct T effector cells (via CD3 binding) to prostate cancer cells expressing PSMA. In addition to binding domains specific for CD3 and PSMA, AMG 160 contains the N-terminus of an immunoglobulin (Ig)G scFc region. The fusion to the Fc domain is a well-established strategy to prolong the half-life of protein therapeutics, such as cytokines, growth factors, and bispecific antibodies, with several approved for the treatment of cancer (Kontermann, 2011).

A detailed description of the chemistry, pharmacology, efficacy, and safety of AMG 160 is provided in the AMG 160 Investigator's Brochure.

[figure not shown]
